### **9.4.1 Treatments Administered**

IP will only be administered to eligible patients by a medically qualified person as per the local and/or state regulations. The range of persons who can administer an IV can be a physician, a physician assistant, nurse, or nurse practitioner, etc, depending on the local and/or state law.

IP should be administered after all efficacy and safety assessments with the exception of assessments specified in this protocol as requiring postdose administration.

The IP will be administered using the provided prefilled syringes in a “slow bolus” injection to an upper extremity vein within approximately 1 to 2 minutes to each study patient.

During IP administration and until completion of postadministration assessments, a licensed physician must be immediately available and in close proximity to the patient(s) to attend to medical emergencies. The facility must have the capabilities, in accordance with the country and/or local regulations/standard of care, to resuscitate a patient in the event of a medical emergency.

At IP administration visits, the patient should not be released from the study center until the following are completed:

- Postadministration pulse rate and BP measures (approximately 15 minutes after administration)
- Patient is clinically assessed and determined to not be at increased risk of suicidality in the opinion of the investigator (or medically qualified subinvestigator)
- Patient is assessed for mental status and is determined to be free of perceptual disturbances or other conditions that would deem them not ready for release from the study center, in the opinion of the investigator (or medically qualified subinvestigator)

- A physician licensed in the country, state, or other local regulatory authority (investigator or subinvestigator) determines that they are medically able to leave the study center and provides written signoff not less than 15 minutes following administration (see IV Administration and Evaluation Notes document in Study Reference Manual)

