**9.5.5.5            *Unscheduled Visits***

Unscheduled visits can be performed if safety concerns arise and at the discretion of the investigator. Additional examinations may be performed as necessary to ensure the safety and well-being of the patients during the study.

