With the exception of endpoints recorded pre or post IP dose and Visit 69/ET MADRS assessments, in the event there are multiple values of the same endpoint on the same date, the last value will be taken as the value for that date. For endpoints reported pre IP dose, in the event there are multiple values of the same endpoint prior to IP dose, the last value prior to the IP dose is taken as the pre-dose value for that date. Similarly, for endpoints reported post IP dose, in the event there are multiple values of the same endpoint after IP dose, the last value will be taken as the post-dose value for that date. For multiple MADRS assessments on the same date for Visit 69/ET, the last MADRS assessment prior to Visit 69/ET on that date will be taken as the value for that date.

The first relapse date for a patient is defined as the earliest assessment date in which any of the relapse criteria mentioned above were met, obtained either from the date recorded on the Relapse CRF (for the primary reasons of "Risk of Suicide", "Need for hospitalization due to worsening of depression" or "Need for alternative treatment for depressive symptoms") or the dates of the corresponding MADRS or CGI-S assessments. For the relapses based on MADRS total score  $\geq 18$  at 2 consecutive visits, the relapse date is defined as the assessment date of the first visit of the 2 consecutive assessments.

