## 14.4 REPEATED OR UNSCHEDULED ASSESSMENTS OF SAFETY PARAMETERS

If end-of-study assessments are repeated or if unscheduled visits occur, the last nonmissing postbaseline assessment will be used as the end-of-study assessment for generating summary statistics. However, all postbaseline assessments will be used for PCS value determinations, and all assessments will be presented in the data listings.

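### By-visit summaries of post-dose safety measures would use the last same-day repeat rather than the scheduled 15-minute reading, and so could understate a transient effect of the injection

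*SAP*

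**What the plan says.** SAP 14.2, after the visit-window tables, sets out how several values of one endpoint on one date reduce to a single value. Endpoints recorded after dosing have their own sentence: "in the event there are multiple values of the same endpoint after IP dose, the last value will be taken as the post-dose value". The sentence does not refer to the scheduled time of the reading. Between dates, the same section does prefer the schedule: within a window it takes the value collected closest to the scheduled day.

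Protocol 9.4.1 lists what must be completed before a patient leaves after an injection:

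- Pulse rate and blood pressure are measured about 15 minutes after administration.
- "Patient is assessed for mental status and is determined to be free of perceptual disturbances" or other conditions that would prevent release, in the investigator's opinion.
- A physician "determines that they are medically able to leave the study center and provides written signoff not less than 15 minutes following administration".

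Protocol 9.5.5.5, on unscheduled visits, adds that "Additional examinations may be performed as necessary to ensure the safety and well-being of the patients during the study".

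SAP 14.4 deals with repeated or unscheduled safety assessments. Its first sentence, on repeated end-of-study assessments and unscheduled visits, says that "the last nonmissing postbaseline assessment will be used as the end-of-study assessment for generating summary statistics". It then says that "all postbaseline assessments will be used for PCS value determinations, and all assessments will be presented in the data listings".

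**The concern.** One post-dose reading is scheduled. A second on the same day is more likely when the first was abnormal or the patient was not yet fit to leave. If so, whether the 15-minute value is kept depends on what that value showed. Patients without a reaction are summarised at about 15 minutes. Patients with one are summarised later, when they have probably settled. That is selection on the outcome, and it pulls a by-visit post-dose mean or change towards no effect. If acute reactions were commoner on rapastinel than on placebo, more rapastinel readings would be displaced and the difference between arms would shrink.

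The 15-minute measurement follows a slow bolus given over about 1 to 2 minutes, so a short-lived change soon after the injection is what it is placed to detect. A rise below a PCS threshold would then be visible only in listings.

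**Working it through.** The plan gives no figure on this point, so there is nothing to reproduce. The check sets the rules side by side and then shows what size of shift is possible under stated assumptions.

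**Which value each output would use when a post-dose reading is repeated on the same day**

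| Output | Rule | Value used |
|---|---|---|
| By-visit post-dose mean or change, if produced | SAP 14.2 | Last reading of the day |
| PCS counts | SAP 14.4 | All postbaseline readings, peak included |
| Listings | SAP 14.4 | All readings |

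Only the first row is affected.

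**Is the repeat linked to the result?** Protocol 9.4.1 gives one measurement time and a release decision based on clinical judgement. It gives no blood pressure or pulse threshold and no instruction to recheck. The link between an abnormal first reading and a repeat is therefore plausible, but it is inferred.

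**Shift in the by-visit mean (illustration).** Shift = share of patients rechecked × mean fall from first to last reading. Neither input is in the documents.

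| Share rechecked | Fall 5 mmHg | 10 mmHg | 20 mmHg | 30 mmHg |
|---|---|---|---|---|
| 2% | 0.1 | 0.2 | 0.4 | 0.6 |
| 5% | 0.25 | 0.5 | 1.0 | 1.5 |
| 10% | 0.5 | 1.0 | 2.0 | 3.0 |
| 20% | 1.0 | 2.0 | 4.0 | 6.0 |

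**A second illustration, with the recheck triggered by the reading.** Assume that the 15-minute systolic change is normal with mean μ and SD 10 mmHg. Assume too that every rise of 20 mmHg or more is rechecked, and that the recheck has mean change 0. With z = (20 − μ)/10:

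- Share rechecked: P = 1 − Φ(z).
- Mean under the last-value rule: μ − [μP + 10φ(z)].

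| μ | z | P | μP + 10φ(z) | Mean under the rule |
|---|---|---|---|---|
| 2 | 1.8 | 3.6% | 0.07 + 0.79 = 0.86 | 1.1 |
| 5 | 1.5 | 6.7% | 0.33 + 1.30 = 1.63 | 3.4 |
| 8 | 1.2 | 11.5% | 0.92 + 1.94 = 2.86 | 5.1 |

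These are upper-end cases, because all rises at or above the trigger are rechecked and all recover fully. If rechecks are also taken to stay below 20 mmHg, the share of by-visit values at or above 20 falls to zero by construction, so that fall is not evidence of anything.

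**PCS counts.** Assume 200 patients per arm (the planned size), a 5% rate of PCS peaks, and 90% recovering on recheck. Using all values gives 200 × 0.05 = 10. Using only the last value would give 200 × 0.05 × (1 − 0.90) = 1. SAP 14.4 prescribes the first, so this count is not reduced.

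**The case against.** A reader might infer that the SAP keeps only the last reading, so that a post-injection rise disappears from the safety evaluation. The documents do not support that. SAP 14.4 uses all postbaseline assessments for PCS determinations and lists every assessment. Its first sentence concerns end-of-study repeats and unscheduled visits, and a recheck at a scheduled dosing visit is neither. The phrase about all postbaseline assessments has no such limit, however, and naturally covers it. Acute reactions also have other routes into the evaluation. Protocol 9.5.2.1 treats clinically relevant physical findings as adverse events, SAP 9.1 tabulates adverse events by treatment group in the double-blind period, and the DSMB reviews safety data (Protocol 9.8).

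A reader might also infer that patients are rechecked until their readings allow release. Protocol 9.4.1 does not say so. The mental-status item is a clinical judgement, not a repeated blood pressure value. Extra examinations are allowed, but under unscheduled visits.

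Three further objections carry weight. The detailed vital-sign sections are not readable, so it cannot be confirmed that a by-visit post-dose table exists or that it lacks its own selection rule. SAP 15.0 limits output to what an abbreviated study report needs. The rule is also prespecified, identical across arms and parallel to the pre-dose rule, and a last value may be a corrected measurement.

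These objections narrow the point and lower the stakes. They do not supply a reason to prefer the last reading over the scheduled one in a by-visit summary, and equal application across arms does not remove a bias that acts only where a reaction occurs.

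**Conclusion.** The point holds for by-visit post-dose summaries of central tendency and any other non-PCS post-dose summary. There, the last-value rule can displace the scheduled 15-minute reading in a way that plausibly depends on that reading, and the bias would run towards no effect. PCS counts and listings are unaffected on the natural reading of SAP 14.4.

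The size is unknown. The ranges of 0.1 to 6.0 mmHg, and of 0.9 to 2.9 mmHg in the trigger example (2.0 − 1.1 and 8.0 − 5.1), rest wholly on assumed recheck shares, spread and recovery. The conclusion assumes that same-day repeats are recorded as values of the same endpoint, that they follow abnormal readings more often than normal ones, and that a by-visit post-dose summary is produced. Severity is low.

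**What to change.** Amend the same-day sentence in SAP 14.2 for safety endpoints recorded after dosing:

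1. In by-visit summaries, use the reading at the scheduled post-dose time: the assessment labelled as the 15-minute one or, if none is labelled, the reading closest to 15 minutes after injection.
2. Wherever a post-dose summary is produced, add the worst post-dose value of the day.
3. State in SAP 14.4 that same-day repeats at dosing visits are included among the postbaseline assessments used for PCS.

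The cost is a short text change, a revised selection flag and slightly more programming. No additional data need be collected. Post-dose summaries may look slightly less favourable. No dose, release condition or other clinical rule changes.

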## 14.4 REPEATED OR UNSCHEDULED ASSESSMENTS OF SAFETY PARAMETERS

If end-of-study assessments are repeated or if unscheduled visits occur, the last nonmissing postbaseline assessment will be used as the end-of-study assessment for generating summary statistics. However, all postbaseline assessments will be used for PCS value determinations, and all assessments will be presented in the data listings.

# 14.5 MISSING SEVERITY ASSESSMENT FOR ADVERSE EVENTS

If severity is missing for an AE that started before the date of the first dose of open-label IP, an intensity of mild will be assigned. If severity is missing for an AE that started on or after the date of the first dose of open-label IP, a severity of severe will be assigned. The imputed values for severity assessment will be used for the incidence summary; the values will be shown as missing in the data listings.

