#### 9.5.2.1.2 *Severity Assessment*

The investigator will provide an assessment of the severity of each AE by recording a severity rating on the appropriate AE reporting page of the patient's eCRF. *Severity*, which is a description of the intensity of manifestation of the AE, is distinct from *seriousness*, which implies a patient outcome or AE-required treatment measure associated with a threat to life or functionality (Section 9.5.2.1.3). Severity will be assessed according to the following scale:

**Mild:** A type of AE that is usually transient and may require only minimal treatment or therapeutic intervention. The event does not generally interfere with usual activities of daily living.

**Moderate:** A type of AE that is usually alleviated with additional specific therapeutic intervention. The event interferes with usual activities of daily living, causing discomfort, but poses no significant or permanent risk of harm to the research participant.

**Severe:** A type of AE that interrupts usual activities of daily living, or significantly affects clinical status, or may require intensive therapeutic intervention.

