## 9.1 ADVERSE EVENTS

AEs will be coded using the Medical Dictionary for Regulatory Activities.

An AE (classified by preferred term) that occurs during the OLTP or thereafter will be considered a treatment-emergent adverse event (TEAE) if it was not present before the date of the first dose of IP in the lead-in study or was present before the first dose of IP in the lead-in study and increased in severity during the OLTP or thereafter. An AE that becomes serious during the OLTP or thereafter will also be considered as TEAE. If more than 1 AE is reported before the date of the first dose of IP in the lead-in study and coded to the same preferred term, the AE with the greatest severity will be used as the benchmark for comparison with the AEs occurring during the OLTP or thereafter that were also coded to that preferred term. An AE that occurs more than 30 days after the date of the last dose of IP will not be counted as a TEAE.

An AE (classified by preferred term) that occurs during the OLTP of the study will be considered a newly emergent adverse event (NEAE) if the AE was not present before the first dose of IP in the OLTP or it was present before the first dose of IP in the OLTP and increased in severity during the OLTP. An AE that becomes serious during the OLTP will also be considered as NEAE. If more than 1 AE is reported before the first dose of IP in the OLTP and coded to the same preferred term, the AE with the greatest severity will be used as the benchmark for comparison with the AEs occurring during the OLTP that were also coded to that preferred term.

An AE (classified by preferred term) that occurs during the DBTP of the study will be considered a newly emergent adverse event (NEAE) if the AE was not present before the first dose of IP in the DBTP or it was present before the first dose of IP in the DBTP and increased in severity during the DBTP. An AE that becomes serious during the DBTP will also be considered as NEAE. If more than 1 AE is reported before the first dose of IP in the DBTP and coded to the same preferred term, the AE with the greatest severity will be used as the benchmark for comparison with the AEs occurring during the DBTP that were also coded to that preferred term.

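### Missing severity of an open-label adverse event is imputed as severe; if that value is the benchmark, later non-serious double-blind events of the same term cannot count as newly emergent

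*SAP*

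**What the plan says.** SAP 14.5 has two imputation rules, split at the first open-label dose. An AE with missing severity that "started before the date of the first dose of open-label IP, an intensity of mild will be assigned". One that "started on or after the date of the first dose of open-label IP, a severity of severe will be assigned". The second rule covers every AE of the open-label period (OLTP), the DBTP and follow-up. On use, the section says: "The imputed values for severity assessment will be used for the incidence summary; the values will be shown as missing in the data listings".

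SAP 9.1 makes a DBTP event an NEAE if its preferred term is new since the first double-blind dose, or if "it was present before the first dose of IP in the DBTP and increased in severity during the DBTP". Where several earlier AEs share the term, "the AE with the greatest severity will be used as the benchmark for comparison with the AEs occurring during the DBTP". There is one exception to the severity condition: "An AE that becomes serious during the DBTP will also be considered as NEAE". The follow-up NEAE rule is built the same way, with events up to and including Visit 70 as the benchmark.

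TEAEs have an earlier reference point. In the SAP an AE is treatment-emergent "if it was not present before the date of the first dose of IP in the lead-in study", or if it was present then and has worsened.

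Protocol 9.5.2.1.2 defines three severity levels. The highest is severe: "A type of AE that interrupts usual activities of daily living, or significantly affects clinical status, or may require intensive therapeutic intervention".

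**The concern.** Assigning the worst grade to an ungraded AE is cautious when that AE is the event being counted. It is the opposite when the AE is the yardstick for a later event, because a high yardstick makes worsening harder to show. In this design an open-label AE plays both parts: it is an event in the OLTP and the benchmark in the DBTP. SAP 14.5 gives it the same imputed grade in both.

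The NEAE table by treatment group is at stake. The DBTP is the only randomized period of this study, and that table is meant to show what is new or worse after randomization. A missing grade in the open-label period could remove a real worsening from it.

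**Working it through.** The plan states no figure on this point, so there is nothing to reproduce. The check sets the rules side by side and goes through the scale.

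**Inputs**
- Scale (Protocol 9.5.2.1.2): mild = 1, moderate = 2, severe = 3.
- Imputed grade for an open-label AE with missing severity (SAP 14.5): 3.
- DBTP rule for a term already present (SAP 9.1): the event is an NEAE if its grade is greater than the benchmark grade, or if it becomes serious in the DBTP.

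**Non-serious DBTP events that qualify, by benchmark grade**

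| Benchmark | Qualifying DBTP grades | Number of 3 |
|---|---|---|
| mild (1) | moderate, severe | 2 |
| moderate (2) | severe | 1 |
| severe (3), recorded or imputed | none | 0 |

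An event that becomes serious qualifies at all 3 grades, whatever the benchmark.

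**What the imputation removes, compared with the unrecorded true grade**
- True grade mild: 2 − 0 = 2 grades lost (moderate and severe).
- True grade moderate: 1 − 0 = 1 grade lost (severe).
- True grade severe: 0 − 0 = 0, nothing lost.

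**What imputing mild as the benchmark would add wrongly**
- True grade mild: 2 − 2 = 0.
- True grade moderate: 2 − 1 = 1 (a moderate event, no worse than before).
- True grade severe: 2 − 0 = 2 (moderate and severe events, no worse than before).

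**Is the imputed grade meant to be the benchmark?** SAP 14.5 says only that it feeds the incidence summary. The SAP summaries that can be seen in section 9.1 are counts by category and by preferred term, and none is by severity. Also, AEs that began before the first open-label dose are not themselves counted in an OLTP incidence. Setting them to mild can therefore matter to an incidence summary only as a benchmark. The pair of rules (low grade before, high grade after) thus reads as NEAE logic for the OLTP. The cut was not moved to the first double-blind dose for the DBTP, so there the direction reverses.

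**Follow-up.** A DBTP AE with missing severity is also set to 3. It then serves as the benchmark for follow-up NEAEs, with the same result of 0 of 3.

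**TEAEs.** The SAP benchmark lies before the lead-in study. An open-label AE is not part of it, so the imputed grade cannot remove a DBTP event from the TEAE tables.

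**Size.** A lost NEAE needs all of the following in one patient: a missing grade on an open-label AE, the same preferred term again in the DBTP, no seriousness, and a grade above the true earlier one. The documents give none of these frequencies, so no number of lost events can be derived.

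**The case against.** The case for leaving the text alone has four parts.

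- **The benchmark use is not written down.** This is correct: SAP 14.5 neither applies the imputed grade to the benchmark nor excludes it. Protocol 9.7.6.1 plans tables by severity, which is the ordinary purpose of such a rule, and the SAP has been cut down for an abbreviated report. The point therefore rests on inference. The mild rule for pre-dose AEs makes that inference strong. If the sponsor means otherwise, the SAP still needs to say so, since two programmers could derive different NEAE tables.
- **The safeguards are real.** DBTP TEAEs are reported by treatment group beside NEAEs, and all AEs are listed with the severity shown as missing. A reader might infer that double-blind events vanish from the randomized safety comparison, or that a blocked term can never be newly emergent. Neither follows: the TEAE tables keep the events, and an event that becomes serious is an NEAE regardless of grade.
- **Size and direction are unknown.** A reader might infer that losses fall mainly on the rapastinel arms, or that terms drop out of the common-AE table. The documents support neither. Effects that recur at unchanged severity are not NEAEs even with a recorded grade, and nothing shows that worsening would concentrate in one arm. The display threshold is 2% in any treatment group, about 0.02 × 200 = 4 patients at the planned arm size, so a loss in one arm does not remove a term that qualifies in another. Investigators must grade every AE and data are queried before lock, so missing grades may be rare or absent.
- **The remedy has its own error.** Imputing mild as benchmark counts some events that did not worsen. This stands, but for a safety table it errs in the cautious direction.

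**Conclusion.** The concern holds in limited form. If the imputed grade is used as the benchmark, which is the natural reading, SAP 14.5 is conservative for OLTP NEAEs and anti-conservative for DBTP and follow-up NEAEs. For a patient and preferred term with a missing earlier grade, 0 of 3 grades of a later non-serious event can count as worsened.

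The effect is confined to the NEAE tables and to that patient and term. It is probably small. It cannot be quantified, because the documents give no rate of missing severity, and it would be zero if no grade is missing. This is a minor correction worth making because it is cheap. It is not evidence that the randomized safety comparison is biased for or against any arm.

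**What to change.** In SAP 14.5, impute by role:

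- When an AE with missing severity started before the period being analysed and serves as the NEAE benchmark, take it as mild. The cut is the first double-blind dose for the DBTP, and at or before Visit 70 for follow-up.
- When an AE with missing severity started in the period being analysed, take it as severe.

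The same text should state that imputed grades are used in deriving NEAE status, which removes the ambiguity.

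The cost is a sentence or two in the SAP and a small change to the derivation. The downside is that one AE can carry two imputed grades, severe as an event and mild as a benchmark. A few events no worse than the true earlier grade may then be counted as NEAEs.
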